## 6.10 Agent Destruction/Disposal

At the completion of investigation, all unused study agent will be returned to NCI, DCP Repository according to the DCP "Guidelines for AGENT RETURNS" and using the DCP form "Return Drug List".

The guidelines and the form are available on the DCP website.

## 7. CLINICAL EVALUATIONS AND PROCEDURES

### 7.1 Schedule of Events

#### SCHEDULE OF EVENTS

Evaluation/ Procedure	Screening	Baseline Visit/ Eligibility Verification	Randomization (within 45 days of qualifying endoscopy) b	Month 1 (+/- 7 days) Phone contact	Months 3,6,9 (+7 days) and Month 15 (+/- 14 days) Phone or mail contact	Month 12 (+/- 30 days) EGD with biopsies. End of treatment	Month 18 (+/- 30 days) EGD with biopsies. Study termination
Informed Consent		X					
Assess Eligibility	X	X					
Baseline History Assessment	X	X a					
Symptom Assessment Questionnaire	X						
Symptom Assessment		X	X	X	X	X	X
Physical Exam		X				X	X
Vital Signs/ Height and Weight c		X				X	X
Laboratory Tests		X				X	
Pregnancy Test d		X	X				
Qualifying EGD with Biopsies		X g				X h	X h
Biomarkers		X				X	X
Concomitant Medications	X	X	X	X	X	X	X
Dispense Study Agent			X In person or by mail		X Mail e		
Collect Study Agent					X i	X	
Review Pill Diary/Record			X	X	X	X	
Adverse Events			X	X	X	X	X
Telephone Contact	X		X b	X	X		
Interval questionnaire					X	X	
Your Health and Well-Being (SF-36) survey		X				X	

a Do not repeat the Baseline History Assessment Questionnaire at Baseline. If participant is registered to study, enter Baseline History Assessment Questionnaire captured at Screening.

b In person or by phone.

c Do not repeat height measurement after Baseline Testing.

d In persons of childbearing potential a serum pregnancy test must be done at the baseline visit. If positive at that baseline visit that participant is a screen failure. Randomization may occur within 21 days from the baseline visit negative pregnancy test without repeating the test. For randomization to occur after this 21 day window from the baseline visit negative pregnancy test date a repeat pregnancy test must be done and must be known to be negative prior to randomization and medication dispensing.

e Study medication is distributed after randomization and at 3, 6, and 9 months only.

f Study medication is collected at 3, 6, 9 and 12 months.

g Qualifying endoscopy.

h A clinically indicated surveillance endoscopy.

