#### 3.3 Intervention Arms

Participants who have successfully completed radiofrequency ablation for BE with or without dysplasia and who have been histologically-confirmed to be free of Barrett's will be randomly assigned to a 12 month intervention with:

Arm A - aspirin 325 mg PO QD

Arm B – aspirin placebo QD

All participants will take proton pump inhibitor in the FDA approved healing dose as clinically

indicated (omeprazole or S-omeprazole 40 mg twice daily, lansoprazole 30 mg twice daily or equivalent).

Participants will continue study agent up to the day of the 12-month endoscopic assessment (see below).

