### **5.2 Aspirin Administration**

Aspirin or aspirin placebo will all be administered once in the morning with a meal. All study agents will be self-administered by the participants. Participants will be given sufficient agent supplies to last for a 3 month period (between phone interviews or mail contacts) plus a short time period beyond their scheduled interview to account for unavoidable scheduling delays.

*First Randomized Pill Bottle:* Participants who continue to be eligible based on qualifying endoscopy and biopsies and interested in study participation will receive a supply of study pills. The supply will be the randomly assigned study agent. Participants will be instructed to start this

new bottle immediately upon receipt and to record the date that the bottle is started. The study agent may be dispensed to the participant at the randomization visit or shipped directly to the participant.

*Subsequent Randomized Pills:* Participants will be instructed to take at least 3 months of pills from each bottle prior to starting their new one and to record the date that the new bottle is started. Bottles containing randomized pills will be mailed in approximately three month intervals adjusting for the previous pill bottle start date. Special shipments will also be made upon request, if, for example, a participant loses their bottle or does not receive their new bottle of pills.

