## 5.7 Adherence/Compliance

Although drug concentration will not be measured in the blood, compliance will be monitored in the following ways:

*Pill diary completion:* Compliance will be monitored by a pill diary that all participants will be asked to complete (see Appendix B). Participants will be asked to mail back their pill diary and their unused agent supplies after each phone call at Month 3, 6, and 9 visits and to bring both their pill diary and their unused agent supplies to the Post-Intervention evaluation at Month 12 visit.

*Dose count:* Randomized participants will receive their initial 3 month (90 pills plus 10 additional pills) supply of study agent at the randomization visit. At Month 3, 6, and 9 visits the participants will be asked to return all full and empty bottles by mail, and to start taking pills from their new 3 month (90 pills plus 10 additional pills) supply that has been mailed to them. After each visit at Months 3, 6, 9 and 12 compliance will be measured as follows:

number of tablets taken (i.e., number of tablets given - number of tablets returned) / number of tablets that should have been taken during that period of time x100 = % compliance.

Compliance (acceptable adherence to study agent) will be defined as ingestion of  $\geq 80\%$  of the planned agent doses for the purposes of secondary data analyses. In cases where the tablets are not returned, the compliance has to be calculated from the calendar. In cases of non-compliance with the study agent, the participant will be reinstructed. The research nurse or study coordinator and the physicians will provide education for participants, indicating when and how should the tablets be administered.

In case of concomitant medications, subjects are asked to contact the study staff in order to check whether any potential interference is expected. Data on drug suspension or interruption will be reported in the CRFs.

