### 7.2.3 Randomization

Subjects meeting the criteria outlined above and whose standard of care surveillance biopsies document absence of residual Barrett's metaplasia or dysplasia will be eligible for randomization which will take place within 45 days of the qualifying endoscopy. The randomization visit may be in person or by phone.

- Randomization: Once registration is complete, eligibility has been confirmed and eligibility CRF is entered into the web application, participants will be assigned a randomization number pre-generated by the database. Participants will be randomized to receive either active agent (aspirin 325 mg) or placebo. Both the participant and the investigator will be blinded to the agent.
- Symptom assessment.
- Concomitant medications.
- Randomized participants will receive a 3-month supply of study agent (90 pills plus 10 additional pills). The drug supply may be mailed to the participant or given to the participant in person.
- Review pill diary and pill intake instructions with the participant. Participants must be instructed to take at least 3 months of pills from their first bottle prior to starting the next bottle and to record the date that the new bottle is started.
- Assess adverse events.

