#### **Months 3, 6, and 9 (+7 days) Phone or mail contact**

- All participants will have a telephone or mail interview every 3 months (+7 days) regarding symptoms possibly related to the agent, illnesses, doctors' visits, hospitalizations, mediations (including aspirin, NSAIDs and over the counter medications), adverse events, and compliance with study tablets.
- After documentation of continued eligibility and compliance, participants will be instructed to return any unused study agent at this time. Prior to Months 3, 6, and 9 (+7 days) visit the site coordinator should mail to the participant their next 3-month supply of study agent or placebo (90 pills plus 10 additional pills). The participant is instructed to take at least 3 months of pills from each bottle before switching to the next bottle.
- Interval questionnaire.
- Adverse Events assessment.
- Concomitant medications assessment.
- Symptom assessment.
- Review pill diary.

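### The bottle-start-date compliance rate in Section 13.6 cannot register missed pills in a participant who switches bottles at the contacts, as 5.7 directs; the same rule can leave a late Month 12 endoscopy off agent

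*Combined protocol and SAP*

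**What the plan says.** **Compliance.** Section 13.6 names two adherence measures. One is self-reported pills per week. The other is a rate for each bottle, worked out from the reported start dates and the number of pills in the bottle, on the stated premise that participants are told to empty one bottle before opening the next. The section ends by setting compliance at 80% or more of planned doses, without saying which measure decides it.

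The operational sections describe something else. At months 3, 6 and 9, Section 5.7 asks participants to "return all full and empty bottles by mail, and to start taking pills from their new 3 month" supply. Section 7.3 says of the same contacts that "participants will be instructed to return any unused study agent at this time". Section 5.7 also defines a third measure, whose numerator is "number of tablets given - number of tablets returned" and whose denominator is the number due in the period. The diary calendar is the fallback when tablets are not returned. The 80% threshold is stated there too, for secondary analyses. Section 13.6 does not mention this count.

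Sections 5.2, 7.2.3, 7.3 and Appendix B set a minimum. In the words of 7.2.3: "Participants must be instructed to take at least 3 months of pills from their first bottle prior to starting the next bottle".

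**Supply.** Section 3.3 says "Participants will continue study agent up to the day of the 12-month endoscopic assessment". Sections 7.1 and 7.4 give that endoscopy a window of 30 days either side of month 12. Footnote e of the Schedule of Events says "Study medication is distributed after randomization and at 3, 6, and 9 months only", and each supply is 100 pills. Section 5.2 adds that later bottles "will be mailed in approximately three month intervals adjusting for the previous pill bottle start date" and that "Special shipments will also be made upon request, if, for example, a participant loses their bottle".

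**The concern.** A rate built from start dates measures how long a bottle lasted. It stands for pills swallowed only if the bottle was emptied. Where leftover pills are mailed back and the next bottle is opened at a scheduled contact, the interval is set by the calendar and the number of pills missed drops out. The 13.6 rate would then overstate compliance in the group summaries, and so would any 80% classification based on it. The measure that does use returned pills, in 5.7, is absent from the analysis section, so an analyst cannot tell which of three measures defines a compliant participant. With 18 evaluable participants per group planned, credible adherence data matter for interpreting a null biomarker result.

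The supply point comes from the same rule. The ten spare pills in each bottle are handed back, so they do not build up towards a late Month 12 endoscopy, which provides the primary, end-of-treatment biopsies.

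**Working it through.** **Inputs.** 100 pills per bottle, one per day (5.7, Appendix B). Contacts at months 3, 6 and 9, each up to 7 days late (7.1, 7.3). Endoscopy at 12 months, up to 30 days late (7.1, 7.4). Compliance threshold 80% (5.7, 13.6).

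**The plan's own figure.** For the self-report measure, 13.6 equates 6 pills a week with 86%. This reproduces: 6/7 = 85.7%. That measure is unaffected by what follows.

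**Start-date rate.** Section 13.6 prints no formula. I take the evident one: pills in the bottle divided by days until the next bottle is started, at one pill due per day.

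*Case A: the participant switches at the contact and returns the rest (5.7, 7.3).* The numerator is always 100 and the interval follows the calendar.

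| Interval (days) | 13.6 rate |
|---|---|
| 90 | 100/90 = 111% |
| 91 | 100/91 = 110% |
| 98 | 100/98 = 102% |
| 125 | 100/125 = 80% |

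The number swallowed does not enter. Suppose 100 pills are given, 90 are due and 45 are taken, so 55 are returned. The 5.7 count is (100 - 55)/90 = 50%; the 13.6 rate is 111%. If 72 of 90 are taken, 5.7 gives 80% and 13.6 again gives 111%. The 13.6 rate falls below 80% only when the interval exceeds 100/0.80 = 125 days.

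*Case B: the participant takes 90 pills before switching, however long that takes (the minimum in 5.2, 7.2.3, 7.3 and Appendix B).* At true adherence *a* the interval is 90/*a* days, so the rate is 100*a*/90 = 1.11*a*.

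| True adherence | Interval (days) | 13.6 rate |
|---|---|---|
| 100% | 90 | 111% |
| 80% | 112.5 | 89% |
| 72% | 125 | 80% |
| 50% | 180 | 56% |

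Missed pills are now registered, with a relative overstatement of about 11%. Participants with true adherence between 72% and 80% would still be classed as compliant. Taking more than 90 pills shrinks the error; taking all 100 removes it.

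**Supply at full adherence, switching at the contacts.** With months of 365/12 days:

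- Bottle 4 starts at month 9, day 274, or day 281 if the contact is 7 days late.
- It lasts 100 days, so it ends at day 374-381, which is 9-16 days past month 12.
- The window closes at 365 + 30 = day 395.
- Gap for an endoscopy on day 395: 395 - 381 = 14 to 395 - 374 = 21 days.

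With 30-day months, bottle 4 ends at day 370-377, the window closes at day 390, and the gap is 13-20 days.

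Missed doses or a late start shrink the gap. With the same contact-based start at 90% adherence, bottle 4 lasts 100/0.9 = 111 days and ends at day 385-392, a gap of 3-10 days. At 80% it lasts 125 days and ends at day 399-406, with no gap. An assumed 7-day mailing delay to the first dose, carried through to later bottles as 5.2 provides, takes 7 days off the full-adherence gap and leaves 7-14.

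**The case against.** The best defence is that the plan sets a minimum number of pills, not a calendar switch. A participant who follows that minimum and misses doses must open the next bottle later, so the start date does carry information. This stands: a reader might infer from Case A that the start-date rate is always blind to missed pills, and Case B shows that it is not. A reader might also infer that 5.2, 7.2.3 and Appendix B contradict 13.6. They do not by themselves, because taking at least three months of pills is compatible with emptying the bottle. The conflict is with the return-and-restart text in 5.7 and the return instruction in 7.3.

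The consequences are also bounded. Section 13.6 limits the start-date data to treatment-group level, to protect the blind. Section 13.8 puts all eligible participants in the main analysis, with a possible exception for those never given agent, and bars subanalyses from supporting efficacy conclusions. Self-reported pills per week is a second measure that does register missed doses.

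On supply, four bottles hold 400 pills. If each were emptied they would reach day 400, past the window. Section 5.1 speaks simply of 12 months of agent, which the routine supply covers. Section 5.2 intends some allowance for scheduling delay, and its special-shipment examples are open-ended, so a late endoscopy is not excluded. All of this stands. It leaves two things unanswered: ten spare pills do not span a 30-day window once earlier leftovers are returned, and nothing prompts a site to ask for more.

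**Conclusion.** The concern holds as an inconsistency between 13.6 and the switch-and-return procedure in 5.7 and 7.3. For participants who switch at the contacts, the 13.6 rate is about 102-111% regardless of missed pills. For those who take at least 90 pills first, the overstatement is at most about 11% relative. Both figures rest on reading the 13.6 rate as pills per bottle over days between starts; the documents do not say how many participants would follow each pattern. What is affected is adherence reporting and any compliance-based secondary analysis.

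A reader might infer that the primary result or the planned power is compromised. The documents do not support that: the main analysis does not use the compliance score, and the sample-size calculation does not involve it.

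The supply point is secondary. At full adherence, with switching at the contacts and no special shipment, an endoscopy on day 395 could follow 14-21 days off agent, contrary to 3.3. It concerns only visits later than about 9-16 days after month 12, and few participants may be affected. The effect on CDX2 cannot be sized, because the documents give neither an offset time for aspirin's effect nor a distribution of visit dates. Nor is this an overall shortage of tablets: the gap comes from how bottles are switched and returned.

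**What to change.** 1. In 13.6, replace the start-date calculation with the returned-tablet count of 5.7, using the diary calendar where tablets are not returned. Keep the self-reported pills per week as a supporting measure.
2. State in 13.6 that this count defines the 80% classification.
3. Reword the bottle rule in 13.6 to match 5.7 and 7.3: new supply started at the month 3, 6 and 9 contacts, remainder returned.
4. In 5.2, name a Month 12 endoscopy scheduled after the last bottle runs out as a reason for a special shipment.

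Items 1 to 3 cost amendment wording only; the tablet count and its fallback are already collected, so no new data field is needed. The count does depend on mailed returns, which is why the calendar fallback should be carried over. Item 4 costs at most about 21 pills for each affected fully adherent participant (395 - 374), in practice one extra bottle through an existing route. A larger month-9 bottle would also work, but the agent supplier would have to package a non-standard size.

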## 7.2 Baseline Testing/Prestudy Evaluation

### 7.2.1 Screening

Eligible participants will be identified from patients undergoing or who have undergone radiofrequency ablation for BE and are participating in or will participate in an ongoing surveillance program. Potentially eligible participants will be identified through database/charts/clinic lists prior to Baseline Visit. A letter may be mailed to potentially eligible participants introducing the study to the patients. If the Site chooses to utilize a letter, the letter will be signed by the Site PI who is familiar to the patient as the doctor following their medical condition. If the Site PI is not the patient's physician who is treating their BE, the letter will be co-signed by the physician who is familiar to the patient. To facilitate screening, the Study Coordinators are advised to call potential participants and introduce the study over the phone, as well as administer the screening questionnaires. However, the study team may choose to administer the questionnaires in person when the participant is seen at the clinic. Screening to identify potentially eligible participants takes place prior to obtaining Informed Consent. The following questionnaires will be administered during Screening:

- Baseline history assessment questionnaire, to include a review of cancer history and previous medical history, previous surgery, chemotherapy, radiation, and other cancer-directed therapy history, family history, demographic information, including age and race, history of allergies or intolerance to aspirin, aspirin containing products or NSAIDs.
- Symptom Assessment Questionnaire, to include a review of the following symptoms: gastrointestinal bleeding, hematemesis, hematochezia, melena, abdominal pain/cramping, heart burn, irregular heart rate/palpitations, chest pain, shortness of breath, edema, itching, constipation, diarrhea, headache, dizziness, drowsiness, lightheadedness, vertigo, easy bruising/bleeding.
- Use of concomitant medications will be collected.

If the participant is found to be potentially eligible for the study, a Baseline visit will be scheduled.

### 7.2.2 Baseline Testing/Eligibility Verification: Consent; Registration; Qualifying EGD with biopsies

The following procedures will be conducted at the Baseline Testing/Eligibility Verification Visit

- Informed consent must be obtained prior to starting any further study procedures.
- Registration: Registration will be completed during the screening period once informed consent has been signed. All consented participants will be assigned a PID number pre-generated by the electronic database. All participants will be entered with the Data Management Initiative (DMI) database and Participating Organizations registry databases as applicable. Participants will also be registered into site-specific registry databases as applicable.
- Enter Baseline history assessment into the DMI.
- Symptoms assessment.
- Participants will be given a "Your Health and Well-Being (SF-36)" survey. If the survey cannot be completed during the visit due to time constraints, the participant may be asked to complete the survey at a later date, but prior to randomization.
- Use of concomitant medications will be collected.
- Physical examination will be performed (to include assessment of vital signs, height and

weight)

- Laboratory tests: CBC (must include hemoglobin, leukocyte count, platelet count) with differential (must include absolute neutrophil count), Creatinine, electrolytes (must include: sodium, potassium), AST/SGOT, ALT/SGPT, TBILI. Standard of care labs are acceptable for use to confirm eligibility if done within 30 days of Qualifying Visit.
- In persons of childbearing potential a serum pregnancy test must be done as part of the baseline visit/eligibility verification and must be negative. If positive the participant is a screen failure. A participant with a negative pregnancy test at that baseline visit maybe randomized up to 21 days from that negative pregnancy test without repeating the test. If randomization occurs after that 21 day period a repeat negative pregnancy test must be done and must be known to be negative prior to randomization and medication dispensing. If pregnancy is found at any time after randomization such participants are not considered screen failures and the proper procedure for taking a participant off study should be followed. See Notes below.
- Esophagogastroduodenoscopy and biopsies will be performed as part of a clinically indicated surveillance exam to document complete eradication of BE and absence of Barrett's metaplasia or associated dysplasia.
- At the time of qualifying and subsequent EGDs standard of care mucosal biopsies will be performed according to the Seattle protocol (4 quadrant biopsies every 2 cm in individuals with a history of metaplasia or low grade dysplasia, every 1 cm in those with a history of high grade dysplasia)
- Additional research study biopsies will be performed as follows: 4 quadrant biopsies 1 cm above the gastroesophageal junction, at a site mid-way through an area defined by the length and location of the original Barrett's segment, and normal-appearing squamous mucosa 2 cm above the upper extent of the original Barrett's segment (2 biopsies in each of 4 quadrants to be snap frozen plus 1 biopsy for formalin fixation and paraffin embedding, or 9 biopsies in each segment, at 3 separate segments, for a total of 27 additional research biopsies).
- Eligibility will be determined by absence of residual Barrett's metaplasia or dysplasia at this qualifying exam as determined by the local Pathology reading.

